7.4. Randomisation, blinding and unblinding

Randomisation will be done via stratified block randomisation by the study sites to ensure participants with similar characteristics such as gender and age are distributed equally in the intervention and control groups. Randomisation will be done with a computer programme with a seed to allow reproducibility. Randomisation will be done with a 1:1 ratio. To prevent predictability of the random sequence, generation of the randomisation sequence is performed by an independent statistician and details of the randomisation generation is unavailable to all investigators. Randomisation will be allocated using sequentially numbered opaque envelopes. Fitness criteria for randomisation (section 8) must be met prior to randomisation.

Patients will be blinded to the study, as they will not be informed of the treatment duration and likely to be sedated and unaware of the treatment regimens. Investigators will be blinded during the assessment of the participants for clinical stability based on the above-described criteria to minimise observer bias. Once conditions for stopping antibiotics are satisfied, the investigator will be unblinded and contact the primary physicians to stop antibiotics. The physicians will remain blinded until they are informed that the participant is suitable to stop antibiotics. Independent assessors, who are assigned to determine pneumonia recurrences, will be blinded from the randomisation arms. This will be achieved by blinding all study details, including randomisation arms, for participants with potential recurrences from these independent assessors.

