This is a non-inferiority trial with a hierarchical noninferiority–superiority hypothesis. The first analysis to be conducted will be for determination of non-inferiority. Only if non-inferiority is established by this primary analysis, a second analysis for superiority will be conducted using closed testing methods without requiring adjustment of the significance level for multiple comparisons. [39] The trial estimates for the primary outcome will be calculated with the absolute risk difference (proportion of participants with the primary outcome in the short arm minus that in the long arm). Hence, non-inferiority will be concluded if the upper boundaries of the one-sided 95% confidence intervals from both unadjusted and adjusted analyses are below the non-inferiority margin. The purpose of using both adjusted analyses on the intention-to-treat and per-protocol populations to determine non-inferiority is to minimise the inflation of type 1 error associated with non-adherence in non-inferiority trials. [40] Superiority will be declared if the entire confidence intervals for all the trial estimates are above zero.

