2.4. Treatment interventions

Randomisation

Randomisation will be done via stratified block randomisation by the study sites to ensure participants with similar characteristics such as sex and age are distributed equally in the intervention and control groups. Randomisation will be done with a computer program with a seed to allow reproducibility. Randomisation will be done with a 1:1 ratio. To prevent predictability of the random sequence, generation of the randomisation sequence is performed by an independent statistician and details of the randomisation generation is unavailable to all investigators. Randomisation will be allocated using sequentially numbered opaque envelopes. Fitness criteria for randomisation must be met prior to randomisation.

Antibiotic choice

Antibiotic treatment for VAP will be tailored to the susceptibility of the pathogen(s) and in accordance to the 2016 IDSA/ATS VAP guideline³. Primary physicians are encouraged to convert initial empirical regimen to narrow- spectrum therapy based on culture results. In culture-negative cases, empirical antibiotic choice should be made depending on local

antibiogram. The study team will not intervene on the antibiotics choices as this is beyond the objectives of the study.

Antibiotic duration

Number of days of antibiotics is calculated from the first day of appropriate coverage according to the susceptibility of at least 1 of the pathogen(s) recovered from respiratory cultures taken within 48h of screening or VAP symptom onset.

For those participants randomised to the intervention (short duration) arm, site investigators should assess the patients daily. Antibiotics should be stopped at

- a) day 3 to 7, if all respiratory cultures during the same episode of VAP are negative, given that the criteria below are satisfied,
- b) day 5 to 7, if any of the respiratory cultures are positive and positivity is attributable to the current episode of VAP, given that the fitness criteria below are satisfied,
 - a. body temperature was $\leq 38.3^{\circ}\text{C}$ (core body temperature measured orally or rectally) or 38.0°C (axillary) for 48 hours, and
 - b. lack of hemodynamic instability (systolic blood pressure ≥ 90 mm Hg without inotropic support or no requirement of inotropic support to maintain systolic blood pressure above 90 mm Hg).

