2.5. Non-inferiority margin and sample size

The study is designed as a hierarchical non-inferiority /superiority trial where, if non-inferiority can be established, superiority will be assessed. The primary outcome is the composite endpoint of mortality and recurrence at 60(± 5) days of the short duration versus

the long duration of antibiotic treatment for VAP. A meta-analysis showed that mortality attributable to VAP ranges from 13.6 to 42.8% in Southeast Asia⁴. Considering that our primary outcome is a composite binary outcome of mortality and recurrence of VAP, we estimate this to be 55%. We derived an absolute non-inferiority margin of 12% with the fixed-margin method, preserving at least 50% of the efficacy of standard treatment in VAP. Using a group sequential design adopting the boundaries proposed by Fleming- Harrington- O'Brien ($R=0.8$)⁵, a maximum of 412 patients will be required to achieve a power of 80% to conclude non-inferiority between the two groups with an one-sided α risk of 5%. As we anticipate a loss to follow-up of up to 10%, we plan to enrol a maximum of 460 patients.

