7. ANALYSES TO ADDRESS PRIMARY AIMS

All analyses will be formed with R⁷. All packages used in the analysis will be cited according with the corresponding version numbers. All analysis code will be published in an open access online repository with the final manuscript.

All primary and secondary outcomes of the study populations will be analysed using both unadjusted and adjusted methods in both the PP and ITT populations. The purpose of using both adjusted analyses on the intention-to-treat and per-protocol populations to determine non-inferiority is to minimise the inflation of type 1 error associated with non-adherence in non-inferiority trials⁸.

Multivariable regressions will be performed with inverse probability weighting, using baseline patient characteristics (study site, age, sex, comorbidities, residence prior to admission, type of ICU admitted to, SOFA score, VAP infection with CRE, maximum heart rate and minimum mean arterial blood pressure on randomisation day, duration of intubation prior to developing VAP, reason for intubation, number of days from first respiratory symptom onset to first day of appropriate antibiotics) as independent variables.

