7.2. Statistical Methods Used for Analysis of Primary Outcome

Based on both the ITT and PP population, the proportions of participants experiencing the primary endpoint will be tabulated by treatment group. If the absolute, upper two-sided 90% CIs around the absolute unadjusted difference is less than 12%, then the criteria of non-inferiority will be met.

A multivariable logistic regression model, will be applied on the ITT population to calculate the estimates of the treatment differences adjusted for baseline patient characteristics described above. Categories with low counts may be combined. For example, in the event of comorbidities with very low counts, these comorbidities may be combined to avoid difficulties with the maximum likelihood estimation of the logistic model. Where no

information has been entered on the comorbidities, the participants will be considered not to suffer from these comorbidities.

For the PP population, inverse probability weighting⁹ will be applied to calculate the estimates of the treatment differences using the same baseline patient characteristics as above.

For these multivariate logistic regression models, residual and predicted values produced from the model will be examined to assess the assumptions of the model. Specifically, the assumption of linearity between the predicted log odds and the covariates is assessed by plotting lowess graphs. The independence of the error terms will be considered. Influential cases are investigated by plotting the standardised Pearson's residuals against the predicted probabilities and the leverage of the individual observations.

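### The 12% non-inferiority limit is applied to a crude risk difference although randomisation is stratified by site: slightly conservative if site event rates differ, and cheap to improve

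*SAP*

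**What the plan says.** **Design.** Protocol 7.4 states: "Randomisation will be done via stratified block randomisation by the study sites". SAP 2.4 repeats this and adds "Randomisation will be done with a 1:1 ratio". Both documents list eight sites, in Singapore, Thailand, Nepal and Brazil.

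**Decision rule in the SAP.** SAP 7.2 works in the intention-to-treat (ITT) and per-protocol (PP) sets and declares non-inferiority on this condition: "upper two-sided 90% CIs around the absolute unadjusted difference is less than 12" per cent. Site plays no part in that interval. The same section then describes a logistic model in ITT "to calculate the estimates of the treatment differences adjusted for baseline patient characteristics described above" and an inverse-probability-weighted analysis in PP. It attaches no threshold to either.

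**Decision rule elsewhere.** Protocol 10.1 concludes non-inferiority if the upper limits of the "one-sided 95% confidence intervals from both unadjusted and adjusted analyses are below the non-inferiority margin". SAP 7 gives a reason for "using both adjusted analyses on the intention-to-treat and per-protocol populations to determine non-inferiority", which implies that adjusted results also decide. The adjustment is made "using baseline patient characteristics (study site, age, sex, comorbidities, residence prior to admission" and further items, so site is in the adjusted analyses.

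**Centre effects.** SAP 7.6 examines these informally with forest plots, limited to centres that randomised into both arms.

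**The concern.** Blocking within site balances the arms site by site, so differences in event rate between sites no longer contribute to the sampling variation of the treatment comparison. A crude two-proportion variance still counts them. The resulting interval is wider than the design requires, its one-sided error falls below the nominal 5%, and some power is left unused.

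The adjusted analyses cannot offset this. The crude limit is the stated criterion in SAP 7.2 and a necessary condition in Protocol 10.1, so a more precise adjusted result cannot rescue a trial whose crude limit crosses 12%. Equal event rates across sites in four countries with different resources would be surprising, although the documents give no site-level rates.

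**Working it through.** **Inputs from the documents (SAP 2.5, Protocol section on the number of participants).** Event rate: "we estimate this to be 55" per cent. Margin 12 points, one-sided alpha 5%, power 80%, maximum 412 patients (206 per arm), 460 with 10% loss.

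**Input not in the documents.** The standard deviation τ of site event rates. I take 0 to 15 points, with 20 as an extreme. For orientation, treating the quoted range of attributable mortality (13.6% to 42.8%) as uniform gives (42.8 − 13.6)/√12 = 8.4 points.

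**1. The plan's own figure.** Crude, unpooled, fixed-sample:

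n per arm = (1.645 + 0.842)² × 2 × 0.55 × 0.45 / 0.12² ≈ 212.5, so 213 per arm and 426 in total.

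Other crude variants come closer to 412: 422 with the Farrington-Manning restricted variance, 408 for a one-sided comparison of 55% with 67%, and 412.2 before rounding with the unpooled formula at a 60% event rate. For loss to follow-up, 412/0.9 = 457.8, so 458 against the stated 460. The group-sequential maximum cannot be rebuilt exactly because the boundary values are not given. The stated 412 is consistent with a crude calculation, and none of these variants uses site.

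Power of the crude rule at 206 per arm with no site variation:

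SE = √(0.495/206) = 0.0490; Φ(0.12/0.0490 − 1.645) = 78.9%.

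**2. Effect of site variation.** Within-site variance = 0.2475 − τ². Then:

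- SE_crude = √(2 × 0.2475/206) and SE_within = √(2 × (0.2475 − τ²)/206)
- power of the crude rule = Φ((0.12 − 1.645 × SE_crude)/SE_within)
- power of the stratified rule = Φ(0.12/SE_within − 1.645)
- one-sided error of the crude rule = Φ(−1.645 × SE_crude/SE_within)

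Example, τ = 10 points: SE_within = √(0.475/206) = 0.0480. Crude power = Φ((0.12 − 0.0806)/0.0480) = 79.4%. Stratified power = Φ(2.499 − 1.645) = 80.3%. Crude error = Φ(−1.679) = 4.7%.

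| τ (points) | 90% half-width, crude / stratified (points) | Power, crude / stratified | One-sided error, crude |
|---|---|---|---|
| 0 | 8.06 / 8.06 | 78.9% / 78.9% | 5.0% |
| 5 | 8.06 / 8.02 | 79.0% / 79.3% | 4.9% |
| 8.4 | 8.06 / 7.95 | 79.2% / 79.9% | 4.8% |
| 10 | 8.06 / 7.90 | 79.4% / 80.3% | 4.7% |
| 15 | 8.06 / 7.69 | 80.0% / 82.2% | 4.2% |
| 20 (extreme) | 8.06 / 7.38 | 81.0% / 84.8% | 3.6% |

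**3. Simulation check.** Eight sites holding about 4% to 25% of patients (assumed), equal arms within site, 206 per arm, 200,000 runs. The crude Wald limit is compared with the Mantel-Haenszel risk-difference limit.

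| τ (points) | Site rates | Power, crude / Mantel-Haenszel | One-sided error, crude / Mantel-Haenszel |
|---|---|---|---|
| 0 | 55% | 79.9% / 79.5% | 5.0% / 5.0% |
| 5 | 48–61% | 80.2% / 80.0% | 4.9% / 5.0% |
| 8.4 | 44–66% | 80.5% / 80.4% | 4.8% / 4.9% |
| 10 | 41–68% | 80.5% / 80.5% | 4.6% / 4.9% |
| 15 | 35–74% | 81.2% / 82.2% | 4.1% / 5.0% |

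The realised gain is about half the formula's at τ = 15 (1.0 against 2.2 points) and essentially nil up to τ = 10. At τ = 15 the proportion of runs passing both limits equals the proportion passing the crude limit (81.2%), so there the crude limit is the binding one.

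**The case against.** A critic would say that this is only a preference for a slightly tighter interval. Site is already in the adjusted analyses, the error is in the safe direction, and the gain is small and depends on an assumed spread. Most of that stands. It rules out three stronger readings that a reader might take from SAP 7.2:

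- **The decision rests on the crude interval alone.** That is the literal sense of SAP 7.2. Protocol 10.1, however, also requires the adjusted limit, and SAP 7 says that the adjusted analyses serve to determine non-inferiority. Taken together, the documents make the crude limit necessary but not the only criterion.
- **The trial falls short of its stated power.** It does not. The 412 is consistent with a crude calculation, and site variation raises the crude rule's power slightly, from 78.9% at τ = 0 to 80.0% at τ = 15.
- **The interval is certainly too wide.** Only if site rates differ, and the documents do not say that they do.

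The critic is also right that stratifying has costs. SAP 7.6 allows for centres that did not randomise into both arms. Mantel-Haenszel gives such a stratum zero weight, so its patients would drop out of an analysis defined as all randomised. Pooling small sites within country does not help Brazil, which has one site. The PP set is selected after randomisation, so the variance argument above, which belongs to ITT, does not carry over directly.

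Timing matters too. SAP 4 requires approval by the data safety and monitoring board (DSMB) for analysis-plan amendments. SAP 2.2 dates the end of follow-up to 14 February 2023, and SAP 9.2 leaves the trial statistician unblinded.

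These points call for a careful pooling rule and a low priority. They do not remove the mismatch between how patients were allocated and how the deciding interval is computed.

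**Conclusion.** The point holds as a minor, low-cost improvement. An interval that must pass under both documents ignores the one stratification factor of the design. For site standard deviations of 0 to 15 points, its one-sided error is about 5.0% to 4.2%, and the power forgone is about 0 to 1 point by simulation, or up to 2 by formula. These figures rest on a 55% event rate, 206 evaluable patients per arm, a fixed-sample approximation and assumed site spreads. If site rates are similar, nothing is lost.

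Because the crude rule errs on the conservative side, this point does not undermine a positive non-inferiority result. What needs settling in any case is that SAP 7.2 ties the margin to one limit, while Protocol 10.1 and SAP 7 bring in others.

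**What to change.** 1. In SAP 7.2 and Protocol 10.1, replace the unadjusted limit with the upper limit of the two-sided 90% interval for the site-stratified Mantel-Haenszel risk difference, in ITT and PP. Report the crude difference descriptively.
2. Fix a pooling rule that depends on site size and allocation only, never on outcome. A site below a stated size, or with patients in one arm only, is merged with another site in its country. A country with a single site is merged with a stratum named in advance. No randomised patient is dropped.
3. In the same edit, list in SAP 7, SAP 7.2 and Protocol 10.1 which limits must be below 12%: stratified and covariate-adjusted, ITT and PP. If the logistic model contributes to the decision, say how a risk difference and its interval are obtained from it.

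The cost is the pooling rule, standard code, and an SAP amendment with DSMB approval. The amendment should be dated and justified as following the randomisation scheme, since the statistician is unblinded. There is no gain if site rates prove similar.

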Participants in the intervention (short duration) arm will receive antibiotics for up to 7 days. Antibiotics should be stopped from day 3 to 7 if respiratory cultures are negative and the patients fulfil a set of stringent clinical criteria signifying cardiopulmonary stability for 48 hours. If the respiratory cultures are positive, patients who fulfil the same set of clinical criteria should have their antibiotics stopped from day 5 to 7 (see section 8. Interventions). Antibiotics administered via all routes i.e. intravenous, oral and nebulisation should be stopped. Randomisation will be carried out when the participants fulfil the clinical stop criteria. The rationale for stopping antibiotics at the above time points is as follows:

Group 1: Short Duration arm

(a) Day 3

Patients who have negative respiratory cultures should have their antibiotics stopped from day 3 to 7 if the patient satisfies a set of criteria signifying clinical stability. As discussed above, though there are no randomised studies to support this, there are 2 observational studies [32, 33] showing that discontinuation of antibiotics in these cases did not result in a higher mortality or rate of new respiratory infections compared to those whose antibiotics were continued. In addition, those whose antibiotics were withheld had a lower rate of total secondary infections by MDROs. One of these studies concluded that antibiotics could be safely discontinued in patients with negative respiratory cultures with no significant impact on mortality, despite persistence of signs and symptoms of pneumonia in 35% of these patients [32]. The above studies have led to the recommendation in the 2016 IDSA/ATS guideline that for patients with suspected VAP whose respiratory invasive culture results are below the diagnostic threshold for VAP, antibiotics should be withheld rather than continued [3].

(b) Day 5-7

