3. QUALITY CONTROL AND DATA VALIDATION

Throughout the trial, data checks will be performed in conjunction with data collection and data entry. Prior to any analysis, the Trial Statistician will perform additional data checks and validations, investigating the data for outliers and inconsistent dates. All apparent outliers will be checked against paper records and either confirmed as valid observations or corrected.

For the final analysis, a manual 100% data entry check of the following variables will be performed by local research staff:

- Dates for enrolment, randomisation, antibiotic durations, discharge, readmissions, intubation and extubations
- Primary outcomes including mortality and pneumonia recurrences
- Secondary outcomes including microbiological cultures, antibiotic susceptibility reports, adverse events

Following this, at least two rounds of queries will be raised by the central data manager based at MORU using the MACRO software to identify possible inconsistencies and missing data.

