5.5. Description of Adherence with Intervention

Adherence with randomised intervention will be carefully assessed since poor adherence may increase type 1 error.

Adherence in the short arm is defined as all antibiotics being stopped 7 days or fewer from the start date of appropriate antibiotics or VAP respiratory symptom onset date, whichever is later. For example, for a participant who started having respiratory symptoms on 1st March 2020, and who was prescribed an appropriate antibiotic (e.g. meropenem) on 2nd March 2020, day 0 for which antibiotic duration is based on is 2nd March 2020. This participant will be considered adherent if all antibiotics (other than, when applicable, anti-tuberculosis antibiotics, prophylaxis e.g. peri or post operative or in immunocompromised hosts, gut prokinetic antibiotics) are stopped by 9th March 2020. Antibiotics are allowed to

be restarted subsequently for clinical indications. The percentage of participants in the short arm for whom antibiotics are restarted will be reported in the final report.

Adherence in the long arm is defined as antibiotics being continued for more than 7 days from the start date of appropriate antibiotics or VAP respiratory symptom onset date, whichever is later. For example, the same participant who started having respiratory symptoms on 1st March 2020, and who was prescribed an appropriate antibiotic (e.g. meropenem) on 2nd March 2020, day 0 for which antibiotic duration is based on is 2nd March 2020. This participant will be considered adherent if any antibiotics (other than, when applicable, anti-tuberculosis antibiotics, prophylaxis e.g. peri or post operative or in immunocompromised hosts, gut prokinetic antibiotics) are continued on or after 10th March 2020.

Antibiotic durations for the index episode of VAP, calculated using the above descriptions, will be presented in a survival plot to show the distribution of the data. This demonstrates how successful the trial intervention is and no statistical analysis will be performed. Total antibiotic duration, classified by short and long arms, during 60-day follow-up will be analysed as a secondary outcome.

The proportion of participants who are non-adherent will be presented in the CONSORT diagram with a breakdown of the actual reasons.

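### The per-protocol weights leave out antibiotic day at randomisation and culture status, although adherence is judged against a fixed day 7/8 cut and so depends on that day

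*SAP*

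**What the plan says.** **Timing of randomisation.** Protocol 5: "Randomisation will be carried out when the participants fulfil the clinical stop criteria". SAP 2.4 sets the stopping window at "day 3 to 7, if all respiratory cultures during the same episode of VAP are negative", and at "day 5 to 7, if any of the respiratory cultures are positive and positivity is attributable to the current episode of VAP". Under SAP 2.7, a patient allocated to the short arm stops on the day of randomisation.

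**Adherence.** SAP 5.5: "Adherence in the long arm is defined as antibiotics being continued for more than 7 days from the start date of appropriate antibiotics" (or from symptom onset, if later). Its worked example makes day 8 the first qualifying day. Short-arm adherence means stopping by day 7. SAP 6 builds the per-protocol population on the same 7-or-fewer and 8-or-more rule.

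**Covariates.** SAP 7 and Protocol 10.1 give one list. The items nearest to this point are "maximum heart rate and minimum mean arterial blood pressure on randomisation day, duration of intubation prior to developing VAP, reason for intubation", and "number of days from first respiratory symptom onset to first day of appropriate antibiotics". SAP 7.2 uses the list for the ITT logistic model and again for the per-protocol population, where inverse probability weighting "will be applied to calculate the estimates of the treatment differences using the same baseline patient characteristics as above".

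**Decision.** Protocol 10.1 requires the unadjusted and the adjusted upper bounds to fall below 12 points, and relies on ITT and per-protocol together to contain the type I error that non-adherence causes. SAP 7.7 plans no further sensitivity analysis.

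**The concern.** A long-arm patient randomised on day 3 must stay on antibiotics five more days to count as adherent; one randomised on day 7 needs one more. In the short arm the slack runs the other way: four days for a patient randomised on day 3, none for one randomised on day 7. Adherence is thus tied to randomisation day, in opposite directions in the two arms.

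If randomisation day also predicts death or recurrence, it confounds the per-protocol comparison. Weights can remove confounding only by variables they contain. The one timing covariate on the list ends on the first day of appropriate antibiotics, which is where the interval that matters begins. Culture status decides whether the window opens on day 3 or day 5, and it is also absent; infection with CRE, which is listed, covers only some positive cultures.

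At stake is the per-protocol analysis as the check on an ITT result that non-adherence may have diluted.

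**Working it through.** **The plan's own figure.** With 55% v 67%, one-sided 5% and 80% power:
(1.645·√(2·0.61·0.39) + 0.842·√(0.55·0.45 + 0.67·0.33))² / 0.12² ≈ 203.2, so 204 per arm or 408 in total, without sequential inflation. The plan states 412. 412/0.9 = 458, against 460 stated. The sample size is not in dispute.

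**Inputs from the documents:** 55% event rate, 12-point margin, one-sided 5%, N = 460 at 1:1, randomisation on days 3 to 7, adherence cut at day 7/8.

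**Inputs assumed, because the documents give none:**
- distribution of randomisation day: flat over days 3 to 7, or weighted to days 5 to 7 (mean 5.52)
- daily chance h of stopping early in the long arm: 2-10%
- daily chance q that stopping is delayed in the short arm: 0-30%
- rise in event risk s per later day: 2-6 points, with 0 as a check
- no help from the other covariates (worst case)

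**Step 1, adherence by randomisation day d.** Long arm: (1 − h)^(8−d). Short arm: 1 − q^(8−d).

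| h | long arm, day 3 | long arm, day 7 | mean day, long-arm per-protocol set (flat; 5.00 at randomisation) |
|---|---|---|---|
| 2% | 90% | 98% | 5.04 |
| 5% | 77% | 95% | 5.10 |
| 10% | 59% | 90% | 5.21 |

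In the short arm the mean day moves down, to 4.96 (q = 10%) or 4.85 (q = 30%).

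**Step 2, bias in short minus long.** Bias = s × (mean day in short-arm set − mean day in long-arm set). For s = 4, h = 5%, q = 10%: 4 × (4.957 − 5.102) = −0.58 points.

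| days | s | h | q | bias (points) |
|---|---|---|---|---|
| 5-7 weighted | 2 | 2% | 0 | −0.06 |
| flat | 4 | 2% | 0 | −0.16 |
| flat | 4 | 5% | 10% | −0.58 |
| flat | 4 | 10% | 10% | −1.01 |
| flat | 6 | 10% | 30% | −2.15 |
| either | 0 | any | any | 0 |

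**Step 3, false non-inferiority at a true 12-point excess, ITT difference held at 12.** Simulation with N = 460 and 3,000 runs per scenario (simulation error about 0.4 points), over scenarios with s of 2 to 6:
- per-protocol alone: 5.4-11.8% without day, 4.1-5.4% with day
- ITT and per-protocol both passing, without day: 4.0-4.6%

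**Step 4, the same with the 12-point excess following treatment received, so that non-adherence dilutes ITT.** Flat days, s 2 to 6, h 2-10%, q 10-30%. With 6,000 runs the simulation error near 5% is √(0.05·0.95/6000) ≈ 0.3 points. Ranges span two separate simulations where both reported the quantity:
- ITT difference: 7.7-11.0 points; ITT alone passes falsely in 8-25%
- per-protocol without day: difference 10.0-11.8 points
- both passing, without day: 5.0-10.3%
- both passing, with day in arm-specific weights: 4.2-5.2%

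**The case against.** The strongest objection is that ITT must pass as well, so a per-protocol bias cannot by itself yield a non-inferiority claim. Step 3 bears this out: with ITT undiluted, the joint rate stays below 5%. But the plan pairs the two analyses precisely because non-adherence dilutes ITT. In that case (step 4) per-protocol becomes the binding test, and without day it errs in the same direction as ITT.

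Three stronger readings are tempting, and the documents do not support them:
- *That the adjusted ITT model is also biased.* Day at randomisation precedes allocation and is balanced by it. Leaving it out costs precision at most.
- *That selection acts in the long arm only.* Short-arm adherence is judged at day 7, not on the randomisation day, so delayed stopping selects there too.
- *That the long-arm set is enriched with slow responders.* A late day may instead reflect a positive culture (the day-5 floor) or recruitment delay (up to 72 hours, Protocol 7.2). No outcome by day is given.

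Other points stand:
- SOFA, CRE, and heart rate and arterial pressure on randomisation day may absorb part of the effect.
- Early stopping in the long arm may be rare: Protocol 3 cites a 12-13 day median in Thailand, and Protocol 12.2 plans contact with physicians to secure adherence. The low end of the range may therefore be nearer the truth.
- Read literally, the 8-day rule drops long-arm patients who die before day 8 but keeps comparable short-arm deaths. If 1%, 3% or 5% of the long arm die in that window, 55% becomes (0.55 − x)/(1 − x), a fall of 0.45, 1.4 or 2.4 points. This is as large as the bias above and opposite in sign.
- Better weights leave the unadjusted per-protocol comparison as it is. The correction reaches the decision because Protocol 10.1 also requires the adjusted bounds to pass; the criterion sentence in SAP 7.2 names only the unadjusted difference.

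**Conclusion.** The point holds for the per-protocol weights. Two variables set before allocation, one directly tied to adherence by the plan's own definitions and the other fixing when the window opens, are missing from the weight model, and no listed covariate replaces them. The per-protocol definition creates the selection; the omission leaves it uncorrected.

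The size is modest and rests on assumptions: roughly 0 to 2 points toward the short arm, out of a 12-point margin, and zero if day is not prognostic. Where non-adherence dilutes ITT, joint false non-inferiority is about 5-10% without day and about 4-5% with it. These figures are worst case as to the other covariates. Because early long-arm deaths could offset or exceed this bias, the net direction is not certain. What can be said is that the safeguard is weaker than it need be. It cannot be said that the trial's conclusion leans toward non-inferiority.

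**What to change.** In SAP 7 and 7.2 and Protocol 10.1:
- Add days of appropriate antibiotics received at randomisation, and culture-positive/negative status, to the per-protocol adherence-weight model, fitted separately in each arm.
- Optionally add both to the ITT model, stating that this is for precision only.
- Report the distribution of randomisation day by arm, in the ITT and per-protocol sets side by side, so that any selection can be seen.

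The cost is SAP and protocol wording. The dates are already subject to the full data-entry check in SAP 3 ("Dates for enrolment, randomisation, antibiotic durations, discharge, readmissions, intubation and extubations"), which also covers microbiological cultures, and SAP 5.5 already derives the start of appropriate treatment. The downside is one or two more terms in the weight model and slightly more variable weights.
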